6.3 MEASURES TO MINIMIZE BIAS: RANDOMIZATION AND BLINDING

A center-stratified randomization method will be used to maintain balance between treatment groups and centers. Equal number of participants per intervention will be considered to maximize study power. The CHKD Pharmacy Department will hold the randomization key and will prepare bottles of study drug and placebo (see Section 6.2.2 Formulation, Appearance, Packaging, and Labeling).

Treating therapists will assign randomization codes in chronological order as participants enroll in the study. Since the study drug and sodium chloride are identical in appearance, the Treating Therapists will

be blinded to study assignment. Those participants assigned to "Group C", or standard PT alone, will be unblinded to treatment as they will not receive iontophoresis.

In the case of an unexpected and serious adverse event in which knowing the study assignment is critical to the medical care of the participant, the CHKD pharmacist may release this information to the Independent Safety Monitor only, who may share this information with the treating physician.

Both the Treating Therapist and the participants assigned to one of the two iontophoresis groups will be blinded to study treatment. The DSP injection and 0.9% sodium chloride injection are clear, colorless liquids that will be supplied by the CHKD Pharmacy Department in identical looking single-use bottles. Each bottle will contain 1.8 mL of solution and will be labeled in a blinded fashion as either lontophoresis Study Drug "A" or "B".

In this study, the Treating Therapists will also perform all physical therapy assessments. While having a separate group of "assessing therapists" and "treating therapists" minimizes bias even further than the current study design, combining their roles is preferred as it reduces error by minimizing the number of therapists involved, improves completion consistency of the RTS Criteria Checklist, and minimizes scheduling conflicts caused when trying to coordinate two therapist's schedules for every study visit conducted.

6.4 STUDY INTERVENTION COMPLIANCE

All participants will be asked to attend up to 12 Study Treatment Visits within an 8-week period. Compliance with this request will be documented by the primary Treating Therapist with assistance from front office staff. The Treating Therapist will review all active study participants at his/her site to ensure each participant attended the two scheduled visits. Any study participants who missed a visit will be contacted by the therapist within 24 hours of the missed visit to be counseled on the importance of maintaining the assigned visit schedule and to ascertain if the participant wishes to continue with the study, as described in section 7.3. Lost to Follow-Up.

Participants and/or parents will be asked to verbally confirm or describe compliance with their HEP, patch wear time (for those assigned to Groups A and B), icing recommendations, activity modifications, and bracing and NSAID use as recommended by their referring physician.

6.5 CONCOMITANT THERAPY

Concomitant therapy during this study to include:

- NSAIDs for pain as recommended by referring physician, if applicable
- Brace use as recommended by referring physician, if applicable
- Ice for pain per standard of care as described on handout provided to all patients

Patients and/or parents will be asked at the beginning of each PT treatment about use of the concomitant treatment options listed above. This will be documented by the treating physical therapist each visit. Each of these concomitant treatments may help reduce pain, but they will be recommended to participants across all three treatment groups, so it is feasible to analyze and distinguish independent effects of the study intervention compared to any potential effects from the concomitant therapies described above.

For this protocol, a prescription medication is defined as a medication that can be prescribed only by a properly authorized/licensed clinician. Medications to be reported in the Case Report Form (CRF) are concomitant prescription medications, over-the-counter medications and supplements.

7 STUDY INTERVENTION DISCONTINUATION AND PARTICIPANT DISCONTINUATION/WITHDRAWAL

7.1 DISCONTINUATION OF STUDY INTERVENTION

Iontophoresis will be discontinued at the earlier of the following time points:

- The participant meets the RTS criteria
- The participant has completed 12 iontophoresis patch applications
- The participant has been receiving iontophoresis treatment for 8 weeks
- The participant develops any medical condition for which full participation in PT (including, but not limited to iontophoresis) would be contraindicated
- The participant meets an exclusion criterion (either newly developed or not previously recognized) that precludes further study participation

Discontinuation from iontophoresis does not mean discontinuation from the study, and remaining study procedures should be completed as indicated by the study protocol. If a clinically significant finding is identified (including, but not limited to changes from baseline) after enrollment, the investigator or qualified designee will determine if any change in participant management is needed. Any new clinically relevant finding will be reported as an adverse event (AE).

The data to be collected at the time of study intervention discontinuation will include the following:

- Brief physical exam of the affected knee
- Adverse event review and evaluation
- Concomitant medication review
- FACES Pain Scale
- RTS Checklist
- 30-day Phone Follow-up
- 90-day Survey Follow-up
- LEFS

Subjects who experience a relapse of pain after the Clinic Check Visit and prior to the 90-day Follow Up will not receive additional iontophoresis treatment as part of the study plan. Subjects who fall into this category will be treated with standard of care treatment as determined by the Treating Therapist or referring physician.

7.2 PARTICIPANT DISCONTINUATION/WITHDRAWAL FROM THE STUDY

Participants are free to withdraw from participation in the study at any time upon request. An investigator may discontinue or withdraw a participant from the study for the following reasons:

- If any clinical adverse event (AE), or other medical condition or situation occurs such that continued participation in the study would not be in the best interest of the participant
- If the participant meets an exclusion criterion (either newly developed or not previously recognized) that precludes further study participation

The reason for participant discontinuation or withdrawal from the study will be recorded on the Early Termination Case Report Form (CRF). Subjects who sign the informed consent form and are randomized but do not receive the study intervention may be replaced. Subjects who sign the informed consent form, are randomized and receive the study intervention, and subsequently withdraw, or are withdrawn or discontinued from the study, will not be replaced.

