2.3 RISK/BENEFIT ASSESSMENT

2.3.1 KNOWN POTENTIAL RISKS

2.3.1.1 Iontophoresis

- May cause mild tingling, prickling and/or warm sensation this is normal and should be anticipated by the participant
- Redness underneath the application site used for iontophoresis
- Dryness or rough skin in area where the iontophoresis was administered
- Skin discoloration or hyperpigmentation

- On rare occasions, iontophoresis therapy can result in transient skin reactions such as rash, inflammation, irritation or burns (blistering). These skin reactions may be the result of:
 - o individual sensitivity to the ionic solution used
 - o the condition of the skin at the onset of treatment
 - o reaction to the materials in the electrodes
 - \circ a poor connection between the electrode and the patient's skin.

Participants will be instructed that if the treatment becomes painful, or if they experience a burning sensation, or an excessive sensation, they should remove the Patch and notify their Treating Therapist.

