5.2 EXCLUSION CRITERIA

An individual who meets any of the following criteria will be excluded from participation in this study:

- 1. Index knee symptomatic for pain only with palpation and not with activities of daily living or while playing sport
- 2. Diagnosis of bilateral apophysitis of the knee where both knees meet all of the inclusion criteria
- 3. Systemic fungal infections
- 4. Has an implanted electronic device
- 5. Has a known sensitivity to DSP
- 6. Presence of damaged skin, denuded skin, or other recent scar tissue on index knee
- 7. Presence of active dermatologic conditions in the affected area (e.g., eczema, psoriasis)
- 8. Presence of an abnormal neurological exam that indicates the subject would have a reduced ability to perceive pain (e.g. peripheral neuropathy)
- 9. Has a known sensitivity to electrical current
- 10. Is currently taking systemic steroids
- 11. Has had iontophoresis with DSP treatment within the past 30 days
- 12. Previously enrolled in this study
- 13. Currently enrolled in another treatment research study

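### Sections 7.1 and 7.2 give one trigger two incompatible consequences, and 7.2 permits patch-related events to end outcome collection in the iontophoresis arms only; the likely effect is small and the repair cheap.

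*Combined protocol and SAP*

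**What the plan says.** Section 7.1 lists the events that end iontophoresis. One is: "The participant meets an exclusion criterion (either newly developed or not previously recognized) that precludes further study participation". The text below that list adds: "Discontinuation from iontophoresis does not mean discontinuation from the study, and remaining study procedures should be completed as indicated by the study protocol". The data to be collected at that point include the RTS Checklist, LEFS, FACES and both the 30-day and 90-day follow-ups.

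Section 7.2 governs leaving the study. It opens: "An investigator may discontinue or withdraw a participant from the study for the following reasons". The second reason is the same trigger in the same words: "If the participant meets an exclusion criterion (either newly developed or not previously recognized) that precludes further study participation". The first reason is an adverse event or other condition that makes continued participation not in the child's interest. Treated children who are withdrawn are not replaced.

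The exclusion criteria in Section 5.2 include number 5, "Has a known sensitivity to DSP"; number 6, "Presence of damaged skin, denuded skin, or other recent scar tissue on index knee"; number 7, active skin conditions in the affected area; and number 9, sensitivity to electrical current. Section 2.3.1.1 says that iontophoresis can, rarely, cause "transient skin reactions such as rash, inflammation, irritation or burns (blistering".

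Only Groups A and B receive iontophoresis (Sections 1.3 and 6.3). In the Schedule of Activities, the Early Stop Visit appears to include FACES, LEFS, the knee examination and adverse event review, but no RTS Checklist. The table is imperfectly rendered, so this should be checked against the original.

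**The concern.** A child in Group A or B who develops a skin reaction or a sensitivity may then meet an exclusion criterion because of the assigned treatment. Under Section 7.1 that child stops the patch and is followed. Under Section 7.2 the same child may leave the study. Nothing says which section governs, so six clinics could handle identical cases differently. A child in Group C cannot reach these criteria through a patch.

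The decision may also sit close to the endpoint. Section 8.2 has the Treating Therapists judge eligibility. Section 6.3 has them perform all assessments, and they know who is in Group C.

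At stake are the later RTS assessments on which the primary endpoint depends, the later questionnaires, and the detection of new adverse events. None of the four criteria in itself prevents a child from being assessed on the RTS Checklist or answering a questionnaire. Section 9.3 keeps treated children in the analysis set, but Section 9.4.2 only says that non-informative censoring will be checked and gives no action if the check fails.

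**Working it through.** **The plan's own figures.** Section 9.2 gives f = 0.28, 80% power and α = 0.05; Section 9.4.1 makes tests two-sided. For a three-group comparison (noncentral F, 2 and N − 3 degrees of freedom, noncentrality N × f²), the smallest N with power of at least 0.80 is 126 (power 0.800). Then 126 × 1.15 = 144.9, rounded up to 145 and to equal arms of 49, gives 147. Both figures reproduce and are not in dispute; they are the base for what follows.

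**The text side by side.**
- Trigger: identical in 7.1 and 7.2.
- Consequence in 7.1: the patch stops, the child stays, and procedures continue.
- Consequence in 7.2: the investigator may withdraw the child from the study.
- Arms in which the patch can cause the trigger: A and B only.

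**Size of the effect.** The documents give no rate of such withdrawals, no SD for time to RTS, and no RTS times for withdrawn children. Assume that a share s of each patch arm is lost, none of Group C is lost for this reason, and the lost children would have taken k SD longer than the rest, with k from 0.5 to 1.0. With complete cases, the observed mean of a patch arm shifts by

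shift = s × k (in SD), for example 0.05 × 1.0 = 0.05.

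The type I error comes from the noncentral F with no true effect, arms of 49(1 − s), 49(1 − s) and 49, and means −sk, −sk and 0. Power uses DSP differing from both controls by d = 0.28 × √(9/2) = 0.594 SD, the difference that corresponds to f = 0.28. The power columns reflect lost numbers only, not the shift.

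| Loss in A and B | Shift against C (SD) | Type I error | Power from 49 per arm | Power after a further 15% loss in all arms |
|---|---|---|---|---|
| 0% | 0 | 0.050 | 0.862 | 0.797 |
| 2% | 0.01–0.02 | 0.050–0.051 | 0.856 | 0.789 |
| 5% | 0.025–0.05 | 0.051–0.056 | 0.846 | 0.778 |
| 10% | 0.05–0.10 | 0.056–0.074 | 0.828 | 0.758 |
| 20% | 0.10–0.20 | 0.073–0.149 | 0.787 | 0.712 |

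A 5% loss is about 5 of 98 children (0.05 × 98 = 4.9). The largest shift there, 0.05 SD, is 0.05 / 0.594 = 8.4% of the design difference.

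**How plausible such losses are.** Section 2.3.3 reports no significant adverse reaction in over 23,000 DSP treatments. The 95% upper bound is 1 − 0.05^(1/23,000) = 0.013% per treatment. With at most 98 × 12 = 1,176 study treatments, that is at most about 0.15 expected significant reactions. The term is not defined there, so milder skin damage that still meets exclusion 6 is not ruled out.

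**The case against.** Several points on the other side stand.

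- Section 7.2 permits withdrawal and limits it to a criterion that rules out further participation. A reader might infer that the two sections are flat opposites, or that 7.2 forces these children out. The text does not support that: 7.1 concerns treatment, 7.2 concerns the study, and loss is possible rather than required. The shared trigger, with its qualifier undefined, still leaves the two consequences unreconciled.
- A reader might infer that recovery itself becomes a ground for removal, through exclusion 1: "Index knee symptomatic for pain only with palpation and not with activities of daily living or while playing sport". That is strained. Recovery is the endpoint, meeting RTS criteria has its own line in 7.1, and follow-up is scheduled after it. Such a route would also be open in all three arms.
- A reader might infer that safety follow-up is lost. Section 8.3.4 follows recorded events to resolution or stabilisation, and the Early Stop Visit appears to include adverse event review, FACES and LEFS. What can be lost is the detection of new events later.
- A reader might infer bias in the blinded comparison. Groups A and B wear the same device at the same settings, and the documents give no evidence that DSP and saline differ in skin reactions.
- A reader might put a figure in days on the bias. The documents give neither a rate nor a delay, and do not say that children with skin reactions recover more slowly. Even the direction is assumed.

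It is also fair that the missing analysis rule for censored children in Section 9 is a separate and probably larger gap, which reconciling these sections does not close.

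**Conclusion.** The point holds in a limited form. One trigger has two incompatible consequences, and 7.2 permits loss of later outcome data for reasons that the patch can cause in Groups A and B but not in C. It mainly concerns the comparisons with PT alone.

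The likely size is small. The documents describe skin reactions as rare, and at 5% selective loss the distortion is minor. It becomes material only at about 10% to 20%, which nothing in the documents suggests. These figures rest on the assumed loss, the assumed delay of 0.5 to 1.0 SD, and a complete-case analysis. The reason to act is that the route is avoidable and cheap to close, not that a large bias is expected.

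**What to change.** Reconcile 7.1 and 7.2 so that meeting an exclusion criterion, or having an adverse event, after randomisation does not by itself end data collection:

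1. Remove the exclusion-criterion bullet from 7.2 as a ground for leaving the study.
2. State that such children, in all arms, continue the scheduled RTS, LEFS, FACES, Godin and adverse event assessments unless consent or assent is withdrawn or the assessments themselves are not in the child's interest. Word the adverse event bullet in 7.2 to agree with this; otherwise the same skin event could still end follow-up by that route.
3. Add the RTS Checklist to the Early Stop Visit in the Schedule of Activities.

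Whether and when the patch stops is for the sponsor to decide and is not addressed here. The cost is a short amendment and a few more completed follow-up forms.

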7.3 LOST TO FOLLOW-UP

A participant will be considered lost to follow-up if he or she fails to return for 3 consecutive scheduled visits or has gone ten (10) days without treatment, whichever comes first, and is unable to be contacted by the study site staff. The following actions will be taken if a participant fails to return to the clinic for a required study visit:

- The site will attempt to contact the participant and reschedule the missed visit within 24 hours of missed visit and counsel the participant on the importance of maintaining the assigned visit schedule and ascertain if the participant wishes to and/or should continue in the study.
- Before a participant is deemed lost to follow-up, the investigator or designee will make every effort to regain contact with the participant (where possible, 3 telephone calls and, if necessary, a certified letter to the participant's last known mailing address or local equivalent methods). These contact attempts will be documented in the participant's medical record or study file.
- Should the participant continue to be unreachable, he or she will be considered to have withdrawn from the study with a primary reason of lost to follow-up.

8 STUDY ASSESSMENTS AND PROCEDURES

8.1 EFFICACY ASSESSMENTS

As Standard of Care:

- All patients who are referred to the participating PT clinics with a diagnosis of apophysitis of the knee and a prescription for PT with iontophoresis will receive a PT Initial Evaluation (IE).
 Per department policy, the PT IE must take place within 90 days of referral date as indicated on the script.
 - The IE includes: review of demographics, medical history, medication regime, strength and balance tests, pain assessment, review of home exercise program, icing instructions, activity restrictions, and bracing and NSAID instructions as recommended by their referring physician.
- After the IE, and as part of standard of care, all participants, regardless of group assignment, will receive a standardized PT treatment progression provided by qualified therapists.
 - As standard of care, PT progression visits may include up to 19 visits
- Clinic Check Visit Two (2) to three (3) business days after a participant is cleared for RTS, or has received treatment for eight (8) weeks, whichever is sooner, the participant will return to the

clinic for the Treating Therapist to confirm the participant remains pain free and able to meet the RTS criteria.

• Physical therapy progression visits to further fine tune mechanics, strength, and stretch may occur after this visit as part of their standard of care.

Study-related:

Study-related procedures will begin on the first PT Treatment Day, which may be the same day as the IE or at the next PT visit, but never before the Consent is signed. If subjects meet inclusion/exclusion criteria and the potential participant consents to participate at the Initial PT Evaluation Visit, the IE and Enrollment/Randomization Study Treatment Visit 1 visits may be combined.

The following procedures/evaluations will be obtained by the Treating Therapists:

- Lower Extremity Function Scale (LEFS) (see Appendix 12.1) a patient reported paper-based questionnaire that asks the patient to choose the level of difficulty of completing 20 different activities. Assessed at Study Treatment Visits 1, 5, 12/RTS Criteria Met Visit, and 30-day Follow Up. Note: the LEFS will be administered over the phone at the 30-day Follow-Up Visit.
- FACES Pain Scale (see Appendix 12.2) a patient reported paper-based questionnaire that asks the patient to choose the face that best represents the pain they are experiencing in their knee. Assessed at the end of each Study Treatment Visit and again at the end of the Clinic Check Visit.
- RTS Criteria Checklist (see Appendix 12.3) a paper-based checklist completed by the Treating
 Therapist to determine whether or not the participant is ready to safely return to sport. The
 checklist was created to include the basic movements typically required for sports activities,
 though these activities are also applicable for return to PE participation and free play, making it
 appropriate for all patients, even those not involved in organized sports. These movements
 include squatting, running, bilateral and unilateral jumping, back pedaling, and quick direction
 changes. The checklist includes qualifying criteria for proper mechanics and requires that all
 activities be pain-free. The checklist was created to assess readiness for sports participation
 without actually requiring that the patient return to sport participation to meet criteria, as not
 all patients participate in organized sports or are in-season year round. The items assessed as
 part of this checklist are all part of normal standard of care for physical therapy. Assessed at
 each Study Treatment Visit and again at the Clinic Check Visit.
- Godin Leisure-Time Exercise Questionnaire (see Appendix 12.4) a paper-based subject self-reporting questionnaire comprised of four (4) items that address the amount of time an individual engages in mild, moderate, and strenuous leisure time physical activity of at least 15 minutes in duration during a typical week. Assessed at Study Treatment Visit 1 and at the 30-day phone follow-up (see Appendix 12.5 30-Day Phone Follow Up) and 90-Day Follow-Up (see appendix 12.6 90-Day Follow-Up Electronic Survey).
- Study Treatment:
 - Iontophoresis (Groups A and B only) ~ 3 minutes in clinic and 2 hours at home The iontophoresis patch will be applied by a trained therapist in blinded fashion for all participants assigned to groups A and B (see section 6.1.2 Dosing and Administration). Performed at Study Treatment Visits 1 12 (Maximum of 12 treatments, maximum of 8 weeks since first Study Treatment Visit, or when RTS criteria are met and confirmed at the Clinic Visit Check, whichever is sooner).
 - For subjects assigned to Group "C" (PT only Group), Study Treatment Visits 1 12 (maximum of 8 weeks since first Study Treatment Visit, or when RTS criteria is met) will

include only their standard PT Treatment Visits: Study Treatment 1 = Standard PT Treatment 1, Study Treatment 2 = Standard PT Treatment 2....).

Note: Participants who initially meet RTS Criteria but fail to meet the RTS criteria when they return for their Clinic Visit Check will continue with their assigned study treatment until the sooner of: they once again achieve RTS criteria, they have received 12 study treatments, or they have received study treatment for eight (8) weeks.

